4.10.2.3.2 Analyses using the PPS

The analyses described in Section 4.10.2.1 and Section 4.10.2.2.1 will be performed for the PPS (instead of the ITT Analysis Set).

4.10.2.3.3 Analysis using mixed multiple imputation for missing responses

Subjects considered non-evaluable due to administration of forbidden medications, or other treatments for LTB-FL will be considered non-responders and subjects considered non-evaluable due to any other reason will be imputed using the 0.058 overall response probability at Week 28 estimated in the watch and wait arm of a published randomized clinical study⁹ which evaluated this treatment approach as compared to rituximab single agent. This supplementary analysis will be performed for the ITT Analysis Set. Both 90% and 95% CI will be calculated for the common BOR up to Week 28 probability difference.

Situations where missing BOR up to Week 28 will either be set to non-response or imputed for this supplementary analysis are given in Table 10.

Table 10 Missing Response Types and Related Decisions

Missing response type	Decision on missing response
Subjects considered non-evaluable due to administration of forbidden medications, or other treatments for LTB-FL	Non-response
Subjects non-evaluable due to any other reason than the reasons stated above (administration of forbidden medication or any other treatment for LBT-FL)	Impute using 5.8% response rate

[name] S.A	
Protocol RI-01-006	Statistical Analysis Plan

The algorithm for this supplementary analysis is described below-

Step 1: Let n_{1m} and n_{2m} be the number of subjects with missing responses in DRL_RI and MabThera[®] treatment groups

Step 2: Generate data X_{1m} from Bin $(n_{1m}, 0.058)$ for DRL_RI treatment group, X_{2m} from Bin $(n_{2m}, 0.058)$ for MabThera[®] treatment group

Step 3: Simulate m=1000 of such trials in step 2

Step 4: Conduct analysis as described in the MI part of Section 4.10.2.2.6

Step 5: Compare the resulting 90% and 95% CIs to (-0.17, 0.17).

4.10.2.3.4 Analysis with imputation under a non-inferiority assumption

For non-evaluable subjects in the DRL_RI treatment group, BOR up to Week 28 will be randomly imputed using a response probability of 0.71, whereas a response probability of 0.88 will be used for non-evaluable subjects in the MabThera[®] treatment group. The expected reference group response rate of 88.0% minus the non-inferiority margin of 17%. This supportive analysis will be performed for the ITT Analysis Set. Both 90% and 95% CI will be calculated for the common BOR up to Week 28 probability difference.

The algorithm for the above sensitivity analysis is described below-

Step 1: Let n_{1m} and n_{2m} be the number of subjects with missing responses in DRL_RI and MabThera® groups

Step 2: Generate data x_{1m} from Bin $(n_{1m}, 0.71)$ for the DRL_RI treatment group and x_{xm} from Bin $(n_{2m}, 0.88)$ for the Mabthera[®] treatment group

Step 3: Simulate m=1000 of such trials in step 2

Step 4: Conduct analysis similar as described in the MI part of Section 4.10.2.2.6

Step 5: Calculate CIs for this combined estimate and see if CI are within (-0.17, 0.17)

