3.2 Definition of Endpoints / Variables

3.2.1 Definition of Efficacy Endpoints / Variables

3.2.1.1 Definition of the Primary Efficacy Endpoint / Variable

BOR up to Week 28 is defined as the best overall response at any radiologic tumor evaluations (based on central radiology review applying the Cheson 1999² response criteria for malignant lymphoma) up to the end of the allowed window for the Week 28 evaluations. Unscheduled and early termination evaluations will be only considered if they are complete and performed up to the end of the allowed window for the Week 28 evaluations.

[name] S.A	
Protocol RI-01-006	

The primary efficacy endpoint used in the statistical analysis is a binary (response / non-response) BOR up to Week 28 version is defined below. The impact of Intercurrent Events on binary BOR up to Week 28 is not described here but in Section 4.10.2.

For subjects with known tumor response at both Week 12 and Week 28, the definition of binary version of BOR up to Week 28 (the primary efficacy endpoint in the statistical analysis) is:

Response at Week 12	Response at Week 28	Binary version of BOR up to Week 28
CR, CRu or PR	Any known	Response
Any Known	CR, CRu or PR	Response
SD or PD	SD or PD	Non-Response

For subjects with a missing / unknown ("unknown" covers "not evaluable", "not available", "subject not anymore in the study", etc.) tumor response at Week 12 or at Week 28 and tumor response known at the other time-point, the definition of binary version of BOR up to Week 28 is:

Response at Week 12	Response at Week 28	Binary version of BOR up to Week 28
CR, CRu or PR	Missing / Unknown	Response
Missing / Unknown	CR, CRu or PR	Response
SD or PD	Missing / Unknown	Non-Response
Missing / Unknown	SD or PD	Non-Response

For subjects with only missing / unknown tumor responses, the definition of binary version of BOR up to Week 28 is:

Response at Week 12	Response at Week 28	Binary version of BOR up to Week 28
Missing / Unknown	Missing / Unknown	• Non-Response for main analysis using the exact score method, sensitivity analysis using stratified Mantel- Haenszel method, and FDA main estimand
		• Missing for sensitivity analyses within the estimand framework (except FDA main estimand) using multiple imputation approaches and for supplementary analyses as described in Section 4.10.2.3

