4.10.2.2.2 Intercurrent Events

Table 1 and Table 2 lists the intercurrent events (ICEs) identified as relevant for BOR up to Week 28 for FDA and EMA respectively.

Table 1 Intercurrent Events for FDA

Intercurrent Event for FDA

Death prior to first post-baseline radiologic tumor examination

Missing scheduled post-baseline radiologic tumor examination up to Week 28 (for reason other than death)

- reason not related to COVID-19 pandemic
- reason related to COVID-19 pandemic

Initiation of forbidden treatment for LTB-FL prior to Week 28 radiologic tumor examination

Concomitant administration of any other experimental drug or a concomitant chemotherapy, anticancer hormonal therapy, radiotherapy, or immunotherapy is prohibited during study participation. This includes administration of rituximab not included in the protocol scheduled treatment. The relevant eCRF data will be reviewed by medical experts to identify forbidden treatments per the above definition. The programming team will use that information to derive the forbidden treatment ICE.

Table 2 Intercurrent Events for EMA

Intercurrent Event for EMA

Death prior to first post-baseline radiologic tumor examination

- reason for death known to be other than progressive disease
- reason for death progressive disease or unknown

Discontinuation of study treatment prior to first post-baseline radiologic tumor examination

- reason not related to COVID-19 pandemic
- reason related to COVID-19 pandemic

[name] S.A Protocol RI-01-006

Statistical Analysis Plan

Intercurrent Event for EMA

Missed or delayed study drug administration prior to Week 28 radiologic tumor examination

- reason not related to COVID-19 pandemic
- reason related to COVID-19 pandemic

Missing scheduled post-baseline radiologic tumor examination up to Week 28 (for reason other than death)

- reason not related to COVID-19 pandemic
- reason related to COVID-19 pandemic

Initiation of forbidden treatment for LTB-FL prior to Week 28 radiologic tumor examination

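### SAP 4.10.2.3.4 imputes at 0.71/0.88 whatever the reason for missingness, so subjects non-evaluable because of other lymphoma therapy, or death from progression or unknown cause, usually become responders

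*SAP*

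**What the plan says.** SAP 4.10.2.3.4 describes an ITT analysis with missing responses filled in under an assumed inferiority of DRL_RI:

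- DRL_RI: "For non-evaluable subjects in the DRL_RI treatment group, BOR up to Week 28 will be randomly imputed using a response probability of 0.71".
- MabThera: "whereas a response probability of 0.88 will be used for non-evaluable subjects in the MabThera" group.
- Origin of 0.71: "The expected reference group response rate of 88.0% minus the non-inferiority margin of 17"%.
- Population: "This supportive analysis will be performed for the ITT Analysis Set".
- Step 1 defines n1m and n2m to "be the number of subjects with missing responses in DRL_RI and MabThera". Step 2 draws binomial counts for all of them. No reason for missingness is mentioned.

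Who counts as missing is set in SAP 3.2.1.1. A subject with no known response at either Week 12 or Week 28 is non-response in the main analysis, the stratified Mantel-Haenszel analysis and the FDA main estimand. The other entry for the same subject reads "Missing for sensitivity analyses within the estimand framework (except FDA main estimand"), and it extends to the supplementary analyses of 4.10.2.3. Unknown responses include those of subjects who have left the study.

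Three other places treat the reason as informative:

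- SAP 4.10.2.3.3, the neighbouring supplementary analysis: "Subjects considered non-evaluable due to administration of forbidden medications, or other treatments for LTB-FL will be considered non-responders". Its Table 10 repeats the rule.
- Protocol 6.7 defines a need for tumour-targeting treatment outside the protocol as disease progression.
- SAP 4.10.2.2.2 lists "Death prior to first post-baseline radiologic tumor examination" and the start of forbidden LTB-FL treatment as intercurrent events, separate from a missing scan. For EMA, Table 2 divides deaths into those known to have a cause other than progression and those due to progression or of unknown cause.

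**The concern.** The analysis is a stress test: subjects whose outcome is not known are assumed to respond at rates that differ by the full margin. That is reasonable where the outcome really is unknown. It is not reasonable for a subject who started other lymphoma therapy, because the protocol already defines that subject as having progressed. The two adjacent supplementary analyses use the same term, non-evaluable, yet one makes this subject a non-responder with certainty and the other makes the subject a responder in 71% or 88% of imputations. A death from progression or unknown cause before any scan is treated in the same way.

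At stake is how the analysis reads as evidence of robustness. If such failures were more frequent on DRL_RI, it would be more lenient than the main analysis in the direction it is meant to test.

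**Working it through.** **Inputs.** Imputation probabilities 0.71 and 0.88 (SAP 4.10.2.3.4); margin ±0.17 (SAP 4.10.2.1); 156 per group (SAP 4.13.2). Let k1 (DRL_RI) and k2 (MabThera) be the ITT subjects who enter the draw because of other LTB-FL treatment, or because of death from progression or unknown cause before any scan. The documents give no values for k1 or k2, so every count below is an assumption.

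**The plan's own figure.** 0.88 − 0.17 = 0.71. It reproduces exactly.

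**Shift relative to non-response.** Each such subject contributes an expected 0.71 or 0.88 responders instead of 0:

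shift = (0.71·k1 − 0.88·k2)/156

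Per subject this is 0.71/156 = 0.46 points on DRL_RI and 0.88/156 = 0.56 points on MabThera.

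| k1 vs k2 (assumed) | Calculation | Shift (points) |
|---|---|---|
| 3 vs 0 | 2.13/156 | +1.4 |
| 5 vs 0 | 3.55/156 | +2.3 |
| 5 vs 2 | (3.55 − 1.76)/156 | +1.1 |
| 2 vs 2 | (1.42 − 1.76)/156 | −0.2 |
| 0 vs 5 | −4.40/156 | −2.8 |

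**Direction.** The shift favours DRL_RI when 0.71·k1 > 0.88·k2, that is, k1 > (0.88/0.71)·k2 = 1.24·k2. With equal counts the rule is slightly unfavourable to DRL_RI.

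**Can it change a conclusion?** An extreme case was simulated: 16 vs 2 such subjects, 4 other missing subjects per arm, and observed rates of 0.85 (DRL_RI) and 0.88 (MabThera). It used 1000 binomial imputations, an unstratified difference with Wald variance, and Rubin's rules.

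- As written: −0.045, 90% CI −0.114 to 0.024, 95% CI −0.127 to 0.038. Both lie inside ±0.17.
- With the 16 and 2 set to non-response: −0.107, 90% CI −0.179 to −0.034, 95% CI −0.193 to −0.020. Both cross −0.17.
- Main-analysis coding of the same data (all missing as non-response): 136 × 0.85/156 − 150 × 0.88/156 = (115.6 − 132.0)/156 = −0.105, Wald 90% CI −0.180 to −0.030. This also crosses −0.17. The SAP's exact score interval would differ somewhat from the Wald interval.

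So the supplementary result can flip, but in this case the main analysis has already failed.

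**The case against.** The strongest defence has four parts.

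- **Other analyses cover it.** The main ITT analysis, the Mantel-Haenszel analysis and the FDA main estimand already code subjects without any known response as non-response. The tipping-point analysis (SAP 4.10.2.3.1) runs every combination of imputations, including all missing DRL_RI subjects as failures with all missing MabThera subjects as responders, which is harsher than the fix proposed here. SAP 4.10.2.3.3 imputes at 0.058, close to non-response. This stands: an excess of DRL_RI failures would not be hidden from a reader of the full report. It does not make 4.10.2.3.4 consistent with Table 10.
- **Few subjects qualify.** One known response at Week 12 or Week 28 is enough not to be missing. Complete early-termination and unscheduled scans count, and the Week 12 window opens on Day 56 (SAP Appendix 5). This also stands; the number may be zero.
- **Part of the text is redacted.** SAP 3.2.1.1 defers intercurrent events to Section 4.10.2, where the estimand tables and 4.10.2.2.6 cannot be read. An event rule applied before n1m and n2m are counted cannot be excluded. However, Step 4 calls on 4.10.2.2.6 only to analyse data already generated, and the visible Steps 1 and 2 carry no exception.
- **Not every death is a lymphoma failure.** A reader might infer that any subject who died before a scan has a known failed outcome. The documents do not support that. Protocol 9.1.3 handles data missing through COVID-19 death as missing data, and SAP Table 2 separates deaths known to have a cause other than progression. The point therefore covers only deaths from progression or unknown cause.

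**Conclusion.** The inconsistency is real but minor. On the visible text, SAP 4.10.2.3.4 imputes as probable responders some subjects whom Protocol 6.7 defines as progressed and Table 10 sets to non-response. It does the same for deaths from progression or unknown cause before any scan.

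Under the assumed counts in the table the shift is at most 2.8 points in either direction against a 17-point margin, and it is zero if no such subject exists. These sizes rest on 156 per arm and on assumed counts.

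Two stronger readings are tempting and should not be drawn. One is that the stress test works backwards: it favours DRL_RI only when k1 exceeds about 1.24·k2, and otherwise it is neutral or harder on DRL_RI. The other is that the equivalence conclusion is at risk: the main analysis and the FDA main estimand do not use this rule, and in the extreme case where the supplementary result flips, the main analysis already fails.

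**What to change.** In SAP 4.10.2.3.4, add a short decision table modelled on Table 10:

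- Non-evaluable because of forbidden or other LTB-FL treatment: non-response.
- Death from progressive disease or unknown cause before the first post-baseline scan: non-response.
- Deaths known to be from other causes, including COVID-19: state the handling explicitly, consistent with Protocol 9.1.3 and SAP Table 2.
- All remaining non-evaluable subjects: draw at 0.71 or 0.88, with n1m and n2m in Step 1 counting only the subjects to be imputed.

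In SAP 4.10.2.3.3, align Step 1 with Table 10 so that it counts only the subjects the table says to impute. This is a minor clarification: at 0.058 the effect is 0.058/156 = 0.04 points per subject.

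The cost is a few sentences and one change to the imputation flag, made before unblinding. No new data are needed, because the SAP already derives the forbidden-treatment event and death and its primary cause are already summarised.

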4.10.2.3.5 Analysis using study treatment received and stratification data as per eCRF

This supplementary analysis attempt to explore the impact of mis-stratification in the randomization process: same analysis (but now for the eCRF CCL) Risk Category Analysis Set and the eCRF Tumor Grade Analysis Set) as for main estimands for FDA and EMA and also for sensitivity analysis will be performed but the analysis steps in those sections 4.10.2.2.1,4.10.2.2.5 and 4.10.2.2.6 will be stratified using strata data per eCRF (instead of per IWRS) and using study treatment received (instead of study treatment as randomized).

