4.4 Analysis Sets

4.4.1 Intention-To-Treat Analysis Set

The Intention-To-Treat (ITT) Analysis Set will include all randomized subjects. The primary efficacy analysis will be based on the ITT Analysis Set.

If a subject received incorrect study drug, i.e., study drug different to the one assigned per the randomization list, the subject will be summarized and analyzed for the study treatment group per the randomization list. If a subject's stratum has been entered incorrectly in the randomization system, i.e., conflicting with the data in the clinical database, the stratum entered in the randomization system will be used for summaries and analyses.

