4.4.6 Immunogenicity Analysis Set

All randomized subjects with at least one immunogenicity sample with a valid result will be included in the Immunogenicity Analysis Set.

4.4.7 eCRF CCI Risk Category Analysis Set

The eCRF CCI Risk Category Analysis Set will include all subjects from the ITT Analysis Set but with study treatment received (even if different from the randomized study treatment) and CCI risk category as per eCRF (even if different from the category used in the stratified randomization).

4.4.8 eCRF Tumor Grade Analysis Set

The eCRF Tumor Grade Analysis Set will include all subjects from the ITT Analysis Set but with study treatment received (even if different from the randomized study treatment) and tumor grade as per eCRF (even if different from the category used in the stratified randomization).

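### The supplementary mis-stratification analysis in SAP 4.10.2.3.5 changes treatment assignment as well as strata, so it cannot isolate the strata effect if any subject received the other drug or none

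*SAP*

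**What the plan says.** SAP 4.10.2.3.5 gives the analysis one purpose: to "explore the impact of mis-stratification in the randomization process". It repeats the stratified sensitivity analysis (4.10.2.2.1) and the main-estimand analyses for FDA and EMA (4.10.2.2.5 and 4.10.2.2.6) with two changes. The steps are "stratified using strata data per eCRF (instead of per IWRS"), and they are run "using study treatment received (instead of study treatment as randomized").

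The two analysis sets it uses are defined in 4.4.7 (risk category) and 4.4.8 (tumour grade). Each takes every ITT subject, but "with study treatment received (even if different from the randomized study treatment"), together with the eCRF value of the stratification factor.

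The ITT rules in 4.4.1 differ on both counts. After a wrong-drug administration, "the subject will be summarized and analyzed for the study treatment group per the randomization list". After a wrong stratum entry, "the stratum entered in the randomization system will be used for summaries and analyses".

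**The concern.** Wrong strata and wrong drug are separate errors. The drug a subject received says nothing about whether the stratum was keyed correctly. When one analysis changes both and the estimate moves, the reader sees one shift with two possible sources.

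Two further consequences follow within this analysis. First, grouping by treatment received gives up the comparison that randomisation protects. Second, the sets are incompletely defined. They include all randomised subjects, yet the SAP allows for subjects who are randomised and not dosed, since the Safety Analysis Set in 4.4.3 requires at least one dose and the ITT set in 4.4.1 does not. Such a subject has no treatment received, and neither 4.4.7 nor 4.4.8 says which arm the subject joins. In the main analysis a subject with no valid post-baseline tumour assessment counts as a non-responder, so leaving one out here would move the estimate for a reason unrelated to strata.

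At stake is whether a robustness check answers its own question. The equivalence decision does not depend on it.

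**Working it through.** No figure in the plan rests on this point, so there is none to reproduce. The check compares definitions and then sizes the effect.

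**Definitions side by side**

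| Analysis | Strata | Treatment |
|---|---|---|
| Main analysis, 4.10.2.1 | none | as randomised (4.4.1) |
| Stratified sensitivity analysis, 4.10.2.2.1 | as used in randomisation | as randomised (ITT set) |
| Main estimands, 4.10.2.2.5 and 4.10.2.2.6 (partly redacted) | IWRS, as 4.10.2.3.5 describes them | as randomised, as 4.10.2.3.5 describes them |
| 4.10.2.3.5 | eCRF | as received |
| eCRF strata with randomised treatment | not found in the readable SAP | |

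The combination in the last row is the one that would isolate mis-stratification.

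**Effect of one subject on the other drug**

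Inputs: 156 per arm (SAP 4.13.2) and 88% as the expected reference response (SAP 4.10.2.3.4). An 80% rate is added as an assumption, because the sample-size rates are redacted. Both arms have the same rate, with r responders each, so the starting difference is 0. One subject moves from MabThera to DRL_RI.

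- Non-responder: r/157 − r/155
- Responder: (r+1)/157 − (r−1)/155

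At 80%, r = 125 (0.80 × 156 = 124.8):
- non-responder: 125/157 − 125/155 = 0.7962 − 0.8065 = −1.03 points
- responder: 126/157 − 124/155 = 0.8025 − 0.8000 = +0.25 points

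At 88%, r = 137 (0.88 × 156 = 137.28):
- non-responder: 137/157 − 137/155 = 0.8726 − 0.8839 = −1.13 points
- responder: 138/157 − 136/155 = 0.8790 − 0.8774 = +0.16 points

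Three non-responders moved in the same direction at 80%: 125/159 − 125/153 = −3.08 points.

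**Effect of leaving out one untreated non-responder** (only if the set were applied that way), DRL_RI arm at 80%: 125/155 − 125/156 = +0.52 points.

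**Comparison with the strata effect**

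A simulation of the Mantel-Haenszel risk difference used 312 subjects, six strata with response rates from 0.70 to 0.90, no true treatment difference, 5% of subjects with a reassigned stratum, and randomly chosen subjects on the other drug. Apart from the 312, all of these are assumptions; the SAP has 18 strata. The table gives the standard deviation of the change from the reference analysis, in percentage points.

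| Subjects on the other drug | Strata only | Treatment only | Both, as written |
|---|---|---|---|
| 0 | 0.36 | 0.00 | 0.36 |
| 1 | 0.34 | 0.51 | 0.61 |
| 3 | 0.35 | 0.87 | 0.94 |
| 6 | 0.35 | 1.26 | 1.32 |

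The mean change with both swaps stayed within 0.03 points of zero, so under random switching the extra movement is noise, not bias. Under these assumptions one discordant subject already contributes more movement than 5% mis-stratification.

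**The case against.** The strongest reply is that nothing is hidden. The heading of 4.10.2.3.5 names both changes, and both set definitions repeat them. It can be read as a deliberate as-treated analysis with eCRF strata whose purpose sentence is incomplete. That stands as to disclosure, but naming two changes does not separate them.

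Discordance may also be rare and visible. IWRS assigns drug matching the randomised arm (protocol 6.4), and randomisation and first dose are meant to fall on the same day (protocol Table 1–1). Kit numbers, protocol deviations and exclusions from analysis sets are listed (SAP 4.9, 4.5, 4.4.9). All of this stands, and it makes the concern conditional. The documents give no counts. They do foresee wrong-drug administration (protocol 6.2.3; SAP 4.4.1 and 4.4.3).

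Much of the estimand text is redacted, so the absence of an analysis with eCRF strata and randomised treatment can be claimed only for the readable SAP.

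A reader might go further than the documents allow in three ways:

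- **That randomisation is broken for the trial.** The decision rule in 4.10.2.1 uses the unstratified exact method on the ITT set by randomised treatment, and 4.10.2.2.1 also keeps subjects as randomised. Only this supplementary analysis departs.
- **That untreated subjects drop out.** The SAP does not say so; it is silent.
- **That each mis-dosed subject can shift the result by 2/156 = 1.3 points.** For a non-responder the shift is about (pA + pB)/156, which nears 2/156 only when both response rates are close to 100%. For a responder it is about (2 − pA − pB)/156, which nears 2/156 only when both are close to 0%.

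**Conclusion.** The point holds in a limited form. The analysis states one aim and makes two changes. If at least one subject received the other drug or no drug, a difference from 4.10.2.2.1, 4.10.2.2.5 or 4.10.2.2.6 cannot be attributed to strata, and this supplementary analysis is then not a randomised comparison. The assignment of randomised but untreated subjects is unspecified. If there is no such subject, the analysis as written and the strata-only version are the same.

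At 156 per arm and an assumed 80 to 88% response in both arms, each mis-dosed non-responder shifts the difference by about 1.0 to 1.1 points and each responder by about 0.2. Against the 17-point margin this is small: 1.03/17 to 1.13/17, or 6 to 7% of the margin per non-responder. It matters because it is large relative to the strata effect under study, a comparison that rests on the simulation's assumed inputs. The primary conclusion is not affected, and the severity is low.

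**What to change.** - In SAP 4.4.7, 4.4.8 and 4.10.2.3.5, keep treatment as randomised and change only the stratum to its eCRF value. Amend the heading of 4.10.2.3.5 to match. Untreated subjects then stay in their randomised arm, and no further rule is needed for them.
- If an as-treated result is wanted, specify it as a separate supplementary analysis with IWRS strata, in subjects who received at least one dose.
- Report, by arm, how many subjects are discordant on stratum and how many on treatment, so that readers can see whether either analysis could differ from its reference.

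The cost is a few lines of SAP text and a simpler derivation for the strata analysis. No new data are needed. The optional as-treated analysis adds one further set of outputs.
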